9.2 Serious Adverse Event

Any AE, due solely to the underlying disease or disease progression, should not be reported as an SAE, unless the study treatment contributed to the AE.

An AE or adverse reaction is considered serious if, in the view of either the Investigator or Sponsor, it results in any of the following outcomes:

• Death;

• Life-threatening AE;

Note: An AE or adverse reaction is considered "life-threatening" if, in the view of the Investigator or Sponsor, its occurrence places the participant at immediate risk of death. It does not include an event that, had it occurred in a more severe form, might have caused death.)

• Requires hospitalization or prolongation of existing hospitalization;

Note: Any hospital admission with at least 1 overnight stay will be considered an inpatient hospitalization. An emergency room visit without hospital admission will not be recorded as an SAE under this criterion, nor will hospitalization for a procedure scheduled or planned before signing of informed consent. However, unexpected complications and/or prolongation of hospitalization that occur during elective surgery should be recorded as AEs and assessed for seriousness. Admission to the hospital for social or situational reasons (eg, no place to stay, live too far away to come for hospital visits) or where this is required for a protocolled assessment will not be considered inpatient hospitalizations.

- A persistent or significant disability/incapacity or substantial disruption of the ability to conduct normal life functions;
- A congenital anomaly/birth defect;
- An important medical event;

Note: Important medical events that may not result in death, be life-threatening, or require hospitalization may be considered an SAE when, based upon appropriate medical judgment, they may jeopardize the participant and may require medical or surgical intervention to prevent 1 of the outcomes listed above. Examples of such medical events include allergic bronchospasm requiring intensive treatment in an emergency room or at home, blood dyscrasias or convulsions that do not result in inpatient hospitalization, or the development of drug dependency or drug abuse.

9.3 Serious Adverse Event Reporting – Procedures for Investigators

9.3.1 Initial Reports

All SAEs occurring from the time of consent until the Safety Visit must be reported within 24 hours of the knowledge of the occurrence (this refers to any AE that meets any of the aforementioned serious criteria). All SAEs that the Investigator considers related to investigational product occurring until the end of the Safety Visit must be reported to the Sponsor.

To report an SAE, complete the SAE Report Form and email the completed SAE Report Form within 24 hours of awareness. An SAE Report Form will be supplied with the study binder.

In addition to reporting the SAE to Sponsor (or designee), the Investigator must also notify the IRB which approved the study according to their requirements. Copies of all correspondence relating to reporting of any SAEs should be maintained in the site's study files and will be checked routinely by the study monitor.

If the Sponsor and the Investigator consider that the SAE is investigational product related (i.e., an adverse reaction) and unexpected it will be reported to the appropriate regulatory authorities by the Sponsor (or designee) within the pre-defined timelines.

9.3.2 Follow-Up Reports

The Investigator must continue to follow the participant until the SAE has subsided or until the condition becomes chronic in nature, stabilizes (in the case of persistent impairment), or the participant dies.

Within 24 hours of receipt of follow-up information, the Investigator must update the SAE form and submit any supporting documentation (eg, deidentified participant discharge summary, autopsy reports), if requested.

9.4 Pregnancy

Pregnancies occurring in a female partner of a participant after the administration of the investigational product require immediate reporting. They must be reported within 24 hours after the Investigator has become aware of the pregnancy. A pregnancy report will be completed and sent within 24 hours of becoming aware of the pregnancy. The Investigator will collect follow-up information regarding the outcome of the pregnancy and any postnatal sequelae in the infant that must also be reported to the Sponsor or designee. Upon awareness of the outcome of the pregnancy, the Investigator must forward a follow-up Pregnancy Report with any relevant information.

If the outcome of the pregnancy meets the criteria for immediate classification of an SAE (e.g., spontaneous abortion, stillbirth, neonatal death, or congenital anomaly), the Investigator will report the event within 24 hours of being notified of the pregnancy report.

9.5 Expedited Reporting

The Sponsor will report all relevant information about suspected unexpected serious adverse reactions that are fatal or life-threatening as soon as possible to the FDA and the IRBs, and in any case no later than 7 calendar days after knowledge by the Sponsor of such a case, and relevant follow-up information will subsequently be communicated within an additional 8 days.

All other suspected unexpected serious adverse reactions will be reported to the FDA and the IRBs as soon as possible but within a maximum of 15 calendar days of first knowledge by the Sponsor.

The Sponsor will also inform all Investigators as required.

10 STATISTICAL METHODS

10.1 General Considerations

A Statistical Analysis Plan (SAP) will be written after finalizing the protocol and prior to database lock. The SAP will detail the implementation of all the planned statistical analysis in accordance with the principal features stated in the protocol. Any deviations from the SAP will be presented in the final clinical study report.

Continuous variables will be summarized by the number of subjects, mean, standard deviation, standard error of the mean, median, 25th quartile, 75th quartile, minimum, and maximum values.

Categorical variables will be summarized using frequency counts and percentages.

10.2 Analysis Sets

10.2.1 Enrolled Analysis Set

The Enrolled Analysis Set will include all participants who signed the ICF and were enrolled into the study. This analysis set will be used for patient disposition summaries.

10.2.2 Safety Analysis Set

The Safety Analysis Set will be used to assess all safety data and will include all participants who receive any amount of ⁶⁴Cu-SAR-bisPSMA.

10.2.3 Full Analysis Set

The Full Analysis Set (FAS) will include all participants who receive any amount of ⁶⁴Cu-SAR-bisPSMA and have ⁶⁴Cu-SAR-bisPSMA PET/CT imaging results from at least one central reader. The FAS will be used for all efficacy analyses.

10.2.4 Biodistribution Analysis Set

The Biodistribution Analysis Set will include all participants in the Safety Analysis Set and have at least one biodistribution measure.

10.3 Determination of Sample Size

The co-primary endpoints include participant-level correct detection rate (CDR) or true positive detection rate and region-level positive predictive value (PPV).

The assumed participant-level CDR of ⁶⁴Cu-SAR-bisPSMA PET/CT imaging is 42% in participants with biochemical recurrence of PC. A sample size of 40 participants is estimated to provide more than 85% power to achieve a lower boundary of a 2-sided 95% exact binomial confidence interval (CI) about the estimated CDR that exceeds 20%. Accounting for a 20% non-evaluable rate (including lost to follow-up), approximately 50 participants will need to undergo ⁶⁴Cu-SAR-bisPSMA PET/CT in this study.

For the co-primary efficacy endpoint of region-level PPV, assuming 65% of participants are estimated to have ⁶⁴Cu-SAR-bisPSMA PET/CT positive findings in this target population and each participant with positive findings has an average of 1.3 positive regions, then 40 participants are expected to produce approximately 34 positive regions. The assumed region-level PPV rate of ⁶⁴Cu-SAR-bisPSMA PET/CT imaging is approximately 65% in all PET positive regions. Therefore, a sample size of 40 participants (i.e., approximately 34 positive regions) is estimated to provide more than 80% power to achieve a lower boundary of a 2-sided 95% exact binomial CI about the estimated region-level PPV that exceeds 40%.

10.4 Analysis Methods

10.4.1 Enrollment and Disposition

Disposition of participants enrolled, treated, and completed the study will be summarized with reasons for study discontinuation for the Enrolled Analysis Set. The number and percentage of participants in each analysis set will also be presented.

10.4.2 Demographic and Other Baseline Characteristics

Baseline characteristics will be summarized for the Safety Analysis Set and the FAS. Demographic and baseline data including age, sex, race, ethnicity, ECOG status, weight, height

and body mass index at baseline will be listed and summarized. Baseline PC characteristics, including but not limited to PC pathology results, PC staging, initial Gleason score, time from initial diagnosis, time from last biochemical recurrence, relevant symptom history, PSA level at baseline, and prior cancer treatment for PC will be summarized.

10.4.3 Prior and Concomitant Medication

Prior and concomitant medications will be coded using the latest version of the World Health Organization Drug dictionary and tabulated by the Anatomical Therapeutic Chemical class and preferred term for the Safety Analysis Set. Any PC treatment during the study will also be summarized in the same manner.

Prior medications are defined as those medications which stopped prior to the administration of the investigational product. Concomitant medication are medications that are taken at least once after the start of the administration of the investigational product.

Prostate cancer treatment received during the study will also be summarized.

10.4.4 Safety Analysis

Safety parameters will include AEs, SAEs, laboratory assessments, vital signs, and ECG analysis. Safety analyses in general will be descriptive and will be presented in tabular format with the appropriate summary statistics.

All safety analyses will be conducted in the Safety Analysis Set.

10.4.4.1 Adverse Event Analysis

Adverse events will be coded using the latest version of Medical Dictionary for Regulatory Activities (MedDRA).

A TEAE is any AE that occurs after the administration of the investigational product.

TEAEs, TEAEs related to investigational product, TEAEs with grade 3 or higher, TEAEs with grade 3 or higher related to investigational product, and treatment-emergent SAEs will be tabulated by MedDRA system organ class and preferred term.

Serious adverse events, AEs leading to study discontinuation and AEs leading to death will be listed by participant.

10.4.4.2 Laboratory Data Analysis

Safety laboratory parameters and corresponding changes from baseline will be presented as descriptive statistics by visit. Shift tables based on the NCI-CTCAE v5.0 toxicity grading will be presented for selected laboratory parameter between baseline and the highest/lowest post-baseline NCI-CTCAE v5.0 toxicity grade. Any clinically significant abnormalities in laboratory values will be listed.

10.4.4.3 Vital Sign Analysis

Vital signs at each scheduled time point and changes from baseline will be summarized using descriptive statistics.

10.4.4.4 Electrocardiogram Analysis

For ECGs, all standard parameters (heart rate, RR, PR, QRS, QT, QTcF, and QTcB as applicable) at each scheduled time point along with changes from baseline will be summarized using descriptive statistics. The incidence of notable ECG changes in maximum absolute QTcF

and QTcB intervals (> 450, > 480, and > 500 ms) over all post-treatment evaluations, as well as in QTcF and QTcB maximum changes from baseline (> 30 and > 60 ms) over all post-dose evaluations will be summarized.

A listing of ECG data will be provided.

10.4.5 Efficacy Analysis

Efficacy endpoints will be assessed using the FAS.

10.4.5.1 Primary Efficacy Analyses

The co-primary efficacy endpoints include the following:

- Participant-level CDR on Day 0 scan;
- Participant-level CDR on Day 1 scan;
- Region-level PPV on Day 0 scan;
- Region-level PPV on Day 1 scan.

CDR on a participant-level for each central reader is defined as the proportion of TP participants out of all scanned participants who had at least 1 evaluable reference standard datapoint (as without any follow-up reference data it is not possible to determine if the participant is TP or not, which may bias the results) and will be calculated as follows: CDR = TP/(all scanned participants with at least 1 evaluable reference datapoints).

Participants without a ⁶⁴Cu-SAR-bisPSMA PET/CT scan at a specific timepoint (Day 0 or Day 1) will be excluded from the participant-level CDR calculation for that timepoint. Participants with non-evaluable participant-level Reference Standard results will be excluded from the CDR calculation.

PPV on a region-level for each central reader is defined as the proportion of TP regions out of all positive regions on the ⁶⁴Cu-SAR-bisPSMA PET/CT scan with corresponding evaluable composite Reference Standard data and will be calculated as follows: PPV = TP/(TP+FP).

Regions that are not positive on the ⁶⁴Cu-SAR-bisPSMA PET/CT scan at a specific timepoint (Day 0 or Day 1) will be excluded for the region-level PPV calculation for that timepoint.

Region	Description of Anatomic Region
1	Prostatic
2	Pelvic lymph nodes
3	Extra pelvic lymph nodes
4	Visceral/soft tissue
5	Bone

The anatomic regions for lesions include the following:

The point estimates of CDR and PPV on Day 0 and on Day 1 will be computed along with the 2-sided 95% exact binomial CIs using the Clopper-Pearson method. The primary efficacy analyses will be performed for each central reader.

The following sensitivity analyses of the participant-level CDR and region-level PPV will be performed:

- •
- Based on all participants in the FAS regardless whether there are reference datapoints collected. Missing data will be handled as follows:
 - Worst-case imputation:
 - For the participant-level CDR on Day 0 and on Day 1 based on FAS, participants with missing/non-evaluable composite Reference Standard data will be imputed as non-true positive and included in the denominator.
 - For the region-level PPV calculation on Day 0 and on Day 1 based on FAS, PET/CT positive regions with missing/non-evaluable corresponding composite Reference Standard data will be imputed as FP and included in the denominator.
 - Tipping Point Analysis:
 - In addition, to examine the impact of missing or non-evaluable composite Reference Standard data and evaluate the robustness of the results, a tipping point analysis will be performed as a sensitivity analysis for participantlevel CDR and region-level PPV based on the FAS, where participants with missing or non-evaluable composite Reference Standard data will be imputed as TP with probability of p ranging from 0 to 1 with an increment of 0.1 (p = 0 corresponds to none of the participants without Reference Standard information in a PET positive region will be imputed as true positive while p = 1 means all participants without Reference Standard information in a PET positive regions will be imputed as TP).

Details of handling of missing data will be fully described in the SAP.

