7.4 Histopathology

Where clinically feasible, histopathology (from image-guided biopsy or surgery [e.g., salvage pelvic lymph node dissection]) should be obtained for as many ⁶⁴Cu-SAR-bisPSMA PET-positive lesions as possible based on the local interpretation of the ⁶⁴Cu-SAR-bisPSMA PET/CT scans. If clinically feasible, the Investigator should make every effort to obtain histopathology for at least one ⁶⁴Cu-SAR-bisPSMA PET-positive lesion **per region**. The biopsy or surgery specimens will be processed and analyzed locally. The local pathologist evaluating the samples will be blinded to the ⁶⁴Cu-SAR-bisPSMA PET/CT results.

The procedure, date of assessment, imaging modality used to guide biopsy (if applicable) and local histopathology result will be recorded on the eCRF.

For participants undergoing image-guided needle biopsy, the needle biopsy images (e.g., CT, transrectal ultrasound-MRI, ultrasound) of the procedure will be sent to central reading center. The instruction for capturing biopsy images and directions for submitting the images to the central reading center is specified in the Image Acquisition Manual.

All histopathology results (and any associated images) acquired within 180 days (± 15 days) of Day 0 must be transferred to the central reading center.

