7.5.2 Assessment of Reference Standard against the ⁶⁴Cu-SAR-bisPSMA PET/CT Results

For the assessment of the Reference Standard against the ⁶⁴Cu-SAR-bisPSMA PET/CT, region-level matching will be used for histopathology, subregion-level matching for imaging and participant-level matching for PSA response to radiation or other salvage focal therapy (refer to Section 7.5.1). Matching of the Reference Standard against the ⁶⁴Cu-SAR-bisPSMA PET/CT results will be completed via statistical programming.

Assessment of **region-level** Reference Standard against the ⁶⁴Cu-SAR-bisPSMA PET/CT results:

- Histopathology: A region that is ⁶⁴Cu-SAR-bisPSMA PET-positive (i.e., includes at least one unequivocal PET-positive lesion) and Reference Standard positive, will be assigned as true positive (TP) for the region-level status.
- Imaging: A subregion that is ⁶⁴Cu-SAR-bisPSMA PET-positive (i.e., includes at least one unequivocal PET-positive lesion) and Reference Standard positive (i.e., includes at least one unequivocal lesion detected on conventional imaging in that subregion), will be assigned as TP. A region that includes at least one TP subregion will be assigned as TP for the region-level status.
- A region that is ⁶⁴Cu-SAR-bisPSMA PET-positive (i.e., includes at least one unequivocal PET-positive lesion) and is Reference Standard negative based on at least 1 evaluable timepoint, will be assigned as false positive (FP) for the region-level status.
- A region that is ⁶⁴Cu-SAR-bisPSMA PET-negative (i.e., no unequivocal PET-positive lesion or only equivocal lesion(s) detected within the subregions) and Reference Standard negative, will be assigned as true negative (TN) for the region-level status.
- A region that has either non-evaluable ⁶⁴Cu-SAR-bisPSMA result for a specific timepoint or has a non-evaluable or inconclusive Reference Standard will not be assigned for that timepoint.

Assessment of **participant-level** Reference Standard against the ⁶⁴Cu-SAR-bisPSMA PET/CT results:

- A participant with at least one TP region AND/OR at least one unequivocal ⁶⁴Cu-SARbisPSMA PET-positive lesion and confirmed PSA response to radiation or other salvage focal therapy, will be assigned as TP for the participant-level status.
- A participant with at least one unequivocal ⁶⁴Cu-SAR-bisPSMA PET-positive lesion who does not meet the above criteria to be deemed TP, will be assigned as FP for the participant-level status.

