CDR and PPV will be summarized by central reader at Day 0 and Day 1 for participants who had at least 1 reference datapoint, and 2-sided 95% exact binomial confidence intervals (CI) using the Clopper-Pearson method. All primary endpoints will be summarized for the FAS (noting that subjects within the FAS without sufficient results to construct the required outcome variable for the endpoint [e.g. a participant without and evaluable reference datapoint cannot contribute to the determination of CDR] will by nature not be included in the respective endpoint analysis) and will be repeated in PP analysis set as supportive analyses.

Histogram panels will be presented displaying the participant-level CDR and region-level PPV by central reader at Day 0 and Day 1 in the FAS analysis set.

September 4, 2024 CONFIDENTIAL Page 29 of 46

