## • Worst-case Imputation:

- For the participant-level CDR on Day 0 and 1, participants with missing, non-evaluable, or inconclusive Reference Standard data will be imputed as non-TP and will be included in the denominator. The results will be presented in same way as the primary analysis for CDR.
- o For the region-level PPV on Day 0 and 1, PET/CT positive regions with missing, non-evaluable, or inconclusive Reference Standard data will be imputed as FP. The results will be presented in same way as the primary analysis for PPV.

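### CDR leaves out PET-negative participants who lack reference data, although they are already known not to be true positives; the estimate then depends on whether reference completeness differs by PET result

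*Protocol*

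**What the plan says.** Protocol 10.4.5.1 defines, for each central reader and each scan day, "CDR = TP/(all scanned participants with at least 1 evaluable reference datapoints". It adds: "Participants with non-evaluable participant-level Reference Standard results will be excluded from the CDR calculation". The rule makes no distinction by PET result, and the reason given is "as without any follow-up reference data it is not possible to determine if the participant is TP or not, which may bias the results". SAP 9.14.1 repeats the formula and remarks that "a participant without and evaluable reference datapoint cannot contribute to the determination of CDR". The endpoint tables (Protocol 2.7.1, SAP 3.1.1) still put all participants with a scan in the denominator.

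The TP definitions are in Protocol 7.5.2 and SAP 7.8. At region level, histopathology makes a region TP if it "includes at least one unequivocal PET-positive lesion) and Reference Standard positive, will be assigned as true positive (TP) for the region-level status"; the imaging route likewise needs a PET-positive subregion. At participant level the definition opens "A participant with at least one TP region AND/OR at least one unequivocal" PET-positive lesion, the second route also requiring a confirmed PSA response to focal therapy. A scan with no unequivocal lesion, or only equivocal ones, is PET-negative.

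Two sensitivity analyses bear on this. In the worst case (SAP 9.14.1.1), "participants with missing, non-evaluable, or inconclusive Reference Standard data will be imputed as non-TP" and stay in the denominator. The tipping point imputes TP with probability p from 0 to 1. The Protocol's explanatory note describes p = 0 and p = 1 in terms of participants lacking reference information in a PET-positive region. SAP 9.14.1.1 describes them in terms of all participants with missing data and omits the 95% CI.

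**The concern.** TP status is unknown without a reference only when the scan is positive. For a given reader and day, a PET-negative participant cannot be TP, so excluding him discards a result that is already known. If PET-negative participants lose reference data more often than PET-positive ones, the denominator shrinks too far and CDR rises; in the reverse case CDR falls.

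The plan contains features that could make completeness depend on PET. Protocol 7.4 asks for histopathology for as many "PET-positive lesions as possible based on the local interpretation of the" scans, and that local reading is unblinded. PSA response to focal therapy can turn only a PET-positive participant into a TP. Participants who receive prohibited treatment may be discontinued early (Protocol 4.4.4), and whether any reference was obtained first may depend on what the scan showed. At stake are the point estimate and the interval coverage of a co-primary endpoint.

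**Working it through.** **The plan's own figures.** Protocol 10.3 and SAP 4.2 assume CDR 42%, 40 evaluable participants, and a lower 95% Clopper-Pearson limit above 20%. At n = 40 the smallest qualifying count is 14 (lower limit 20.6%). P(X ≥ 14) at 0.42 is 85.5%, which agrees with the stated power of more than 85%. 40/0.80 = 50 scanned, also as stated.

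**Inputs.** Detection rate DR = 0.65, CDR = 0.42 and 20% non-evaluable all come from Protocol 10.3. The implied participant-level PPV is 0.42/0.65 = 0.646. Of 50 scanned, 32.5 are PET-positive, 17.5 PET-negative and 10 non-evaluable. The documents do not say how the 10 divide by PET result, so the split is an assumption and the whole range is shown. Within the PET-positive group, verification is taken as unrelated to true status.

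**Formula.** Let r+ and r− be the shares with an evaluable reference among PET-positive and PET-negative participants. Then

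planned CDR = DR × PPV × r+ / [DR × r+ + (1 − DR) × r−].

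Under the assumption just stated, this equals DR × PPV only if r+ = r−.

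**Results for a true CDR of 42%.** Expected TP = (32.5 − missing PET-positive) × 0.646.

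| Missing PET− / PET+ | TP | Planned (TP/40) | Worst case (TP/50) | All unverified PET+ counted TP (/50) | SAP wording at p = 1, all 10 counted TP (/50) |
|---|---|---|---|---|---|
| 10 / 0 | 21.0 | 52.5% | 42.0% | 42.0% | 62.0% |
| 7 / 3 | 19.06 | 47.7% | 38.1% | 44.1% | 58.1% |
| 5 / 5 | 17.77 | 44.4% | 35.5% | 45.5% | 55.5% |
| 3.5 / 6.5 | 16.8 | 42.0% | 33.6% | 46.6% | 53.6% |
| 0 / 10 | 14.54 | 36.3% | 29.1% | 49.1% | 49.1% |

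DR × PPV is 0.65 × 0.646 = 42.0% in every row. That follows from the assumption about verification among PET-positive participants; it is not independent evidence for the method.

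**Interval coverage.** The nominal 95% Clopper-Pearson interval around the planned CDR, with 50 scanned, covers the true value as follows. The two ends of each range take PPV as 0.646 or rounded to 0.65.

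- r+/r− of 80/80%: 96–97%
- 90/61%: 91–93%
- 95/52%: 85–88%
- 100/43%: 76–80%
- 70/99%: 92–93%

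A percentile bootstrap for DR × PPV covers about 93–96%.

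**What the sensitivity analyses recover.** Worst-case imputation treats PET-negative participants correctly but sets every unverified PET-positive participant to non-TP, so it is a lower bound. The tipping point read as in the Protocol note (only PET-positive participants imputed) gives, at p = 0.6 and 0.7, 41.4% and 42.7% with equal completeness, 41.1% and 43.1% when all 10 missing are PET-positive, and 42.0% when all are PET-negative. Under the SAP wording, p = 1 can reach 62% where 42% is the most attainable.

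**A tempting half-fix.** Restoring PET-negative participants while still dropping unverified PET-positive ones biases CDR downward. With equal completeness it gives 16.8/(50 − 6.5) = 38.6%.

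**The case against.** Four points on the other side carry weight.

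- **Follow-up imaging is universal.** Protocol 7.3.3 and 8.1.4.1 require it whatever the PET result, and one evaluable datapoint is enough. Histopathology adds to this and is not the only source. The splits that leave about half or more of PET-negative participants without any reference are extreme, and nothing in the documents supports them. This stands: the size is unknown and may be small.
- **Direction.** A reader might infer that the bias most plausibly flatters the agent, because biopsies follow positive scans. The documents do not support that. A PET-positive participant who starts prohibited treatment before verification may be discontinued and lose his reference, which lowers CDR.
- **Existing sensitivity analyses.** A reader might infer that nothing planned addresses the issue. That goes too far: the Protocol's tipping-point note comes close to the remedy below. What remains is that the SAP wording drops the PET-positive restriction and gives no interval. The SAP defers programming details of the status algorithm to a supplement that is not in the documents, so the code may be narrower than the text.
- **The 20% limit.** A reader might turn the bias into a false-success rate against 20%. SAP 4.1 plans no formal hypothesis test, and 20% appears only as a sample-size criterion.

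It is also fair that DR × PPV rests on its own assumption. If 80% of TP, 90% of false-positive and 73.4% of PET-negative participants are verified, complete-case CDR is 0.336/(0.336 + 0.207 + 0.257) = 42%, while DR × PPV is 0.65 × 0.336/0.543 = 40.2%. Neither estimator is best under every pattern of missingness.

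**Conclusion.** The concern holds in a limited form. The stated reason for the exclusion is wrong for PET-negative participants on the plan's own definitions, and known non-detections leave the CDR denominator. If completeness differs by PET result, and verification among PET-positive participants is otherwise unrelated to true status, the complete-case CDR is biased. On the plan's rates the possible range is about 36% to 52.5% for a true 42%, with no bias at equal completeness. Those ends are limits set by an assumed split of the 20% non-evaluable, not forecasts. Neither direction nor size can be read from the documents. The planned sensitivity analyses help in part: worst case is a lower bound, and the tipping point would largely cover the issue if the SAP kept the Protocol's PET-positive restriction.

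**What to change.** 1. In Protocol 10.4.5.1 and SAP 9.14.1, correct the rationale: for a given reader and day, a PET-negative participant is known to be non-TP, and only PET-positive participants without an evaluable reference are undetermined.
2. Pre-specify, per reader and day, a CDR over all scanned participants equal to DR × participant-level PPV. This counts unverified PET-negative participants as non-TP and unverified PET-positive participants as TP at the observed PPV. Give a participant-level bootstrap 95% CI. Make it at least the first sensitivity analysis beside the complete-case CDR.
3. In SAP 9.14.1.1, confine the CDR tipping point to PET-positive participants, matching the Protocol note.
4. Report the number without an evaluable reference by PET result, per reader and day, and reconcile the denominators in the endpoint tables with those in the analysis sections.

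The cost is wording and a few lines of code, with no new data; DR and participant-level PPV are already secondary endpoints (SAP 9.14.2). The downside is that the interval is no longer exact binomial, verified PET-positive participants must represent unverified ones, and the reported CDR may move either way.
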